1.3 Additional Exploratory Objectives

- d. To investigate whether daily duloxetine improves functioning, pain, and stiffness in the knees/hips according to the Western Ontario and McMaster Universities Osteoarthritis (WOMAC) scale;
- e. To investigate whether daily duloxetine improves function, pain and stiffness in the hands according to the Modified Score for the Assessment and Quantification of Chronic Rheumatoid Affections of the Hands (M-SACRAH);
- f. To investigate whether daily duloxetine improves functional quality of life as measured by the Functional Assessment of Cancer Therapy-Endocrine Scale (FACT-ES);
- g. To investigate whether daily duloxetine improves the proportion of patients reporting changes for the better versus worst as measured by the Global Rating of Change Scale;
- h. To investigate whether daily duloxetine improves/decreases analgesic use;
- i. To investigate whether daily duloxetine improves/increases adherence to, and reduces the discontinuation rate for, aromatase inhibitor (AI) therapy.
- j. To assess whether patients receiving duloxetine as compared to placebo have improved depression as measured by the Patient Health Questionnaire (PHQ-9) at Weeks 6 and 12 (for patients experiencing depression at baseline).
- k. To explore the relationship between inherited variants in genes responsible for duloxetine metabolism and activity (COMT, HTR3A, SLC6A2, SLC6A4, CYP1A2, CYP2D6) and aromatase (CYP19A1) and change in pain with 12 weeks of treatment.
- l. To explore the impact of treatment on serum inflammatory cytokine levels with 12 weeks of treatment at baseline and 12 weeks.
- m. To bank blood samples for future correlative analyses.

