No effective pharmacologic therapy has yet been identified for management of these symptoms, as many patients do not experience relief of symptoms with analgesic therapy. The current treatment for AIMSS is limited to oral analgesics and exercise. Neither has optimal effect, and long term use of oral analgesics is problematic. Six weeks of acupuncture therapy has been shown to be beneficial compared to sham acupuncture, but long-term benefit of this treatment is unclear. (6)

Investigators at the University of Michigan recently conducted a Phase II open-label clinical trial of duloxetine in 35 postmenopausal women who had been treated with AI therapy for at least 2 weeks and who developed new or worsening pain after starting AI therapy (details below). This definitive multi-institutional randomized, placebo-controlled Phase III trial is founded upon the positive results of the pilot study.

Duloxetine.

Duloxetine is a selective serotonin- and norepinephrine-reuptake inhibitor (SNRI) which is FDA-approved for the treatment of major depressive disorder (MDD), diabetic peripheral neuropathic pain, generalized anxiety disorder, fibromyalgia, and chronic musculoskeletal pain, including osteoarthritis (OA) and low back pain. (7-14) Small uncontrolled studies have also demonstrated that it is potentially effective for treatment of menopausal symptoms and sleep disturbances. (17,18)

Multiple duloxetine doses and schedules have been studied in these various clinical scenarios. (10,11,13,22) In general, duloxetine 60 mg daily was effective and relatively well tolerated in the majority of trials. Some studies demonstrated improved tolerability with a dose-escalation rather than initiation of treatment at the effective dose. Improvement in pain control occurred rapidly in all studies, which typically demonstrated a partial response within 1 to 2 weeks and near maximal response within 6 weeks. In studies of patients with fibromyalgia, the improvement in BPI average pain score was independent of the presence of major depressive disorder.

A small study demonstrated a possible effect of duloxetine therapy on menopause-related symptoms in women with depression. (18) In the 14 postmenopausal patients with MDD who completed the study, improvement was noted in vasomotor, sleep, and anxiety symptoms. Overall pain and pain interference also improved significantly compared to baseline.

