Patients will be instructed to complete the following questionnaires at the Day 15, 43, 85, and 169 visits. It takes about 20-25 minutes to complete the questionnaires.

S1202 Brief Pain Inventory Short Form (BPI-SF)

S1202 Western Ontario and McMaster Universities Osteoarthritis (WOMAC) Index (Version 3.1)

S1202 Modified-Score for the Assessment and Quantification of Chronic Rheumatoid Affections of the Hands (M-SACRAH)

S1202 FACT – ES Trial Outcome Index (Version 4)

S1202 Global Ratings of Change in Joint Pain and Stiffness

Patients will also be instructed to complete the following self-administered questionnaire at the Day 43 and 85 visits. It takes about 5-10 minutes to complete the assessment.

S1202 Patient Health Questionnaire-9 (PHQ-9).

The nurse or CRA will also complete the **S1202** Cover Sheet for Patient-Completed Questionnaires at each visit to indicate whether or not the patient completed the questionnaires, if the patient required assistance and the method for completing the questionnaires. If one or more of the questionnaires was not completed, an overall reason must be indicated on the Cover Sheet. See [Section 15.2](#) for detailed instructions for administration of the questionnaires.

Additionally, at the Day 85 visit, blood will be drawn for serum biomarkers (see [Section 15.1](#)).

All patients must taper off study drug after the Day 85 visit by decreasing the dose to 1 capsule daily for 7 days. After completing the taper of the study drug, if a patient wishes to take commercially-available duloxetine, she should take at least 7 days of duloxetine 30 mg daily prior to increasing the dose to 60 mg daily, in order to minimize the chance of developing side effects. She is permitted to start this at any time following completion of the taper of the study drug (Day 92).

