11.3 Secondary Endpoints

The following secondary analyses will be conducted:

- a. Multiple linear regression analyses of the individual assessment timepoints will be conducted to identify potential critical effectiveness timepoints and to allow comparisons to other studies. These analyses will include the baseline score (as a covariate) as well as the pre-specified stratification factors.
- b. At weeks 2, 6, and 12, we will investigate whether duloxetine 60 mg daily:
 1. Decreases worst joint pain according to the BPI.
 2. Improves functioning, pain, and stiffness in the knees/hips according to the Western Ontario and McMaster Universities Osteoarthritis (WOMAC) scale. Differences between the two study arms of at least two points on the WOMAC Index are of interest. [\(50, 51\)](#) We will also evaluate clinically meaningful change for the WOMAC Index with respect to the $\frac{1}{3}$ to $\frac{1}{2}$ standard deviation during the study period of 12 weeks.
 3. Improves function, pain and stiffness in the hands according to the Modified Score for the Assessment and Quantification of Chronic Rheumatoid Affections of the Hands (M-SACRAH). Differences between the two study arms of at least two points on the M-SACRAH are of interest. [\(50,51\)](#) We will also evaluate clinically meaningful change for the M-SACRAH with respect to the $\frac{1}{3}$ to $\frac{1}{2}$ standard deviation during the study period of 12 weeks.
 4. Improves functional quality of life as measured by the Functional Assessment of Cancer Therapy-Endocrine Scale (FACT-ES).[\(52,53\)](#) Trial Outcome Index (TOI). Clinically meaningful change in FACT-ES TOI scores will also be based on $\frac{1}{3}$ to $\frac{1}{2}$ of a standard deviation. [\(53-55\)](#)
 5. Improves the proportion of patients reporting changes for the better versus worst as measured by the Global Rating of Change Scale. The GRCs for joint pain and for joint stiffness will be used to identify patients who report they are worse (combining scores of -1 through -3), the same score (score of 0), or better (combining scores of +1 through +3) since the last time they completed the questionnaire. [\(54-56\)](#) Mean scores for the WOMAC Index, BPI, M-SACRAH, and FACT-ES TOI will be compared for groups based on those patients who select “a little better” and “a little worse” on the GRC ratings to identify minimally important change. [\(54-56\)](#)

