15.2 Patient Questionnaires: Instructions for Administration

- a. It is important to note that the time frame for providing ratings differs depending on the scale the patient is completing. The **S1202** BPI-SF, **S1202** WOMAC Index, **S1202** M-SACRAH, **S1202** FACT-ES TOI, and **S1202** PHQ-9 should be rated with respect to the past 7 days. The **S1202** Global Ratings of Change in Joint Pain and Joint Stiffness are answered with respect to the last time the patient filled out the questionnaire.

If treatment is delayed for any other reason, the assessment schedule for the Day 15, 43, 85, and 168 assessments should be defined from the treatment start date.

- b. Administration of Questionnaires
 1. The first time the patient completes the questionnaires: Please read to the patient the instructions attached to each patient questionnaire. Explain the specific administration times for this protocol. Patients should be directed to report all symptoms and limitations whether or not they are related to the cancer or its treatment.
 2. It is permissible to assist patients with completing the questionnaires being careful not to influence the patient's response. Note on the **S1202** Cover Sheet for Patient-Completed Questionnaires what assistance was required and indicate reason (e.g., elderly, too sick, etc.). Discourage family members from: 1) being present while the patient completes the questionnaire and/or 2) influencing patient responses to the questions.
 3. It is very important to review the questionnaires after the patient has completed them to be sure all of the questions have been answered and that only one answer is marked. a) If the patient has marked more than one answer per question, ask the patient which answer reflects how she is feeling. b) If the patient has skipped a question, tell the patient that a question was not answered and ask if she would like to answer the question. Always give the patient the option to refuse. Indicate on the form by the question that the patient did not want to answer this question.

4. If a patient refuses or cannot complete the questionnaire for some reason, then this must be documented on the **S1202** Cover Sheet for Patient Completed Questionnaires and submitted to the Data Operations Center in Seattle (see [Section 14.3](#)).

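### The Global Rating of Change is rated since the previous questionnaire, so the Week 12 arm comparison would miss almost all of a sustained benefit, and Week 6 would show only what was gained after Week 2

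*Combined protocol and SAP*

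**What the plan says.** Objective 1.3g reads: "To investigate whether daily duloxetine improves the proportion of patients reporting changes for the better versus worst". Section 11.3b sets the analysis times, "At weeks 2, 6, and 12, we will investigate whether duloxetine 60 mg daily", and item 5 completes that sentence with "Improves the proportion of patients reporting changes for the better versus worst as measured by the Global Rating of Change Scale". Item 5 defines worse, same and better by the patient's rating "since the last time they completed the questionnaire". Section 15.2a gives the same frame to the staff who administer the form: the ratings "are answered with respect to the last time the patient filled out the questionnaire". Two sections agree, so this is the intended design and not a slip.

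On timing, Section 7.2b says "Patients will be instructed to complete the following questionnaires at the Day 15, 43, 85, and 169 visits", and the Global Rating is on that list. It is not among the baseline questionnaires in Section 7.2a. Section 11.3 assigns logistic regression to binary outcomes. It does not re-anchor the rating to baseline or combine successive ratings.

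Item 5 also uses the rating as an anchor for minimally important change: "Mean scores for the WOMAC Index, BPI, M-SACRAH, and FACT-ES TOI will be compared for groups based on those patients who select" a little better or a little worse.

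On time course, the Background says of earlier duloxetine studies that pain control improved rapidly in all of them, "which typically demonstrated a partial response within 1 to 2 weeks and near maximal response within 6 weeks". Table 1 in the Background gives mean average pain in the pilot of 5.5 at baseline and 2.5, 2.1, 2.3 and 2.1 at Weeks 2, 4, 6 and 8.

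**The concern.** The objective is about benefit from treatment, but the rating measures change between adjacent visits. For the other scales, regression on the visit score with the baseline score as covariate estimates the benefit accumulated by that visit. The Global Rating has no such reference point. The better-versus-worse proportion therefore means something different at each of the three visits, although 11.3b treats it as the same outcome measured three times.

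What is at stake is the reading of a flat Week 12 result. Week 12 is the trial's primary assessment time, and it is where this endpoint is least able to register a benefit that arose earlier and lasted. The anchor analysis has a smaller, related problem: a rating of change over one interval should be paired with score change over that interval, and the text says only mean scores.

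**Working it through.** **1. The plan's own figure.** The documents give no power, sample size or expected proportions for the Global Rating. The primary sample size, which supplies the number per arm used below, reproduces. With SD 2.3, two-sided alpha 0.05 and 80% power, n per arm = 2 × (1.960 + 0.842)² × 2.3² / 1.0² ≈ 83 (84 rounded up; plan 83). For a difference of 0.85, 83.0 / 0.85² ≈ 115 (plan 115). Then 230 / 0.85 ≈ 270.

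**2. What each rating covers.** Day 15: start to Week 2. Day 43: Weeks 2 to 6. Day 85: Weeks 6 to 12.

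**3. Pilot pain split into those intervals.**
- Start to Week 2: 5.5 − 2.5 = 3.0 points, which is 3.0 / 3.4 = 88% of the fall to Week 8.
- Weeks 2 to 6: 2.5 − 2.3 = 0.2 points (6%).
- Weeks 6 to 8: 2.3 − 2.1 = 0.2 points (6%).

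**4. Illustrative model of the arm difference.** BPI improvement over an interval is taken as normal with SD s = 2.3 × √(2(1 − ρ)), and a patient is rated better if the improvement is at least c points. Then P(better) = Φ((μ − c)/s). In the duloxetine arm, μ is increased by the effect times the share of it gained in that interval. From the documents: SD 2.3, effect 0.85 to 1.0, 115 per arm. Assumptions not in the documents: ρ 0.5 to 0.7, c 0.5 to 1.0, placebo improvement of 1.0 point by Week 2 and none afterwards, and the share of effect reached by each visit.

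Worked case: effect 0.85, ρ = 0.5 (so s = 2.3), c = 1.0, with 50% of the effect by Week 2 and 95% by Week 6.
- Week 12, rated from the start: Φ((1.85 − 1.0)/2.3) − Φ(0) = 0.644 − 0.500 = 14.4 points.
- Week 6 as planned: added effect 0.45 × 0.85 = 0.38; Φ((0.38 − 1.0)/2.3) − Φ(−1.0/2.3) = 0.394 − 0.332 = 6.2 points.
- Week 12 as planned: added effect 0.05 × 0.85 = 0.04; 0.339 − 0.332 = 0.7 points.

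Arm difference in better, in percentage points, over all settings of effect, ρ and c:

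| Share of effect reached | Week 2 | Week 6 as planned | Week 12 as planned |
|---|---|---|---|
| 100% by Week 2 | 13.5 to 21.3 | 0 | 0 |
| Pilot course (88%, then 94% by Week 6) | 12.1 to 19.0 | 0.8 to 1.3 | 0.8 to 1.3 |
| 75% by Week 2, 100% by Week 6 | 10.3 to 16.3 | 3.4 to 5.5 | 0 |
| 50% by Week 2, 95% by Week 6 | 7.0 to 11.1 | 6.2 to 9.9 | 0.7 to 1.1 |
| 33% by Week 2, 90% by Week 6 | 4.7 to 7.3 | 7.9 to 12.6 | 1.4 to 2.2 |

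Rated from the start of study drug, the Week 12 difference is 13.5 to 21.3 points on every row, with power 0.58 to 0.92 at 115 per arm. As planned, Week 12 power is 0.03 to 0.05, no better than the significance level. Week 6 power reaches at most 0.48, on the last row.

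**The case against.** The strongest objection concerns Week 6. A reader might infer that the Week 6 comparison would also show nothing. The documents do not support that. The Background describes only a partial response at 1 to 2 weeks, and Section 7.1 starts two capsules on Day 8, so Day 15 follows about one week at that level. If onset is gradual, Week 6 can show a larger difference than Week 2, as the last row of the table does. The pilot cannot settle the matter: it had one arm, was open-label, counted 29 evaluable patients and required pain of at least 4 at entry, so its early fall mixes treatment effect with placebo response and regression to the mean. This objection stands. Any calculation that puts the whole effect in by Week 2 returns zero later by construction, which is why onset is varied above.

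A reader might also infer that the endpoint cannot answer objective 1.3g. That is too strong. The objective names neither a time point nor a baseline reference. Week 2 speaks to it, Week 6 does so where onset is gradual, and later ratings could show a difference if the placebo response wanes, which the model leaves out.

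Nor would a flat Week 12 rating stand alone. The longitudinal BPI model adjusted for baseline, the per-visit regressions and the 2-point responder analysis all measure benefit from baseline. The rating is exploratory under 1.3 and is not among the Section 10 outcomes. This limits the harm, but it does not make the Week 12 comparison informative about sustained benefit.

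On the anchor analysis, the stated aim is minimally important change, so mean scores may simply be loose wording for mean change. That part is mostly a clarification.

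**Conclusion.** The point holds for Week 12 and, to a degree that depends on onset, for Week 6. With a sustained benefit that is near maximal by Week 6, the planned Week 12 comparison would show about no arm difference: 0 to 2.2 points, against 13.5 to 21.3 if rated from the start of study drug. Both time courses in the documents lead there. The Week 6 comparison leaves out whatever was gained by Week 2. It would show about 1 point under the pilot course, and roughly 3 to 13 points under the partial-response courses examined.

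The direction at Week 12 follows from the recall frame and the schedule. The percentages rest on the assumed correlation, cut-off, placebo course and onset shares, and are illustrative only. The Week 2 comparison is largely sound, although with no baseline form listed, the last completion has no literal meaning at Day 15. A missed visit would lengthen the interval being rated. The primary BPI analysis is not affected, so this should be corrected but does not threaten the trial's main conclusion.

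**What to change.** Preferred: for the arm comparison, ask at every visit about change since the start of study drug. This also gives Day 15 a defined reference and removes the dependence on missed visits. The cost is rewording the form in English and Spanish, and a longer recall period. No visits or patients are added.

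If the form stays as it is, or has already been used, revise only the text of 11.3b.5:
- Analyse and report the Week 6 and Week 12 ratings as interval change (Weeks 2 to 6 and Weeks 6 to 12), not as benefit at that visit.
- Keep the Week 6 comparison under that label. Restricting the arm comparison to Week 2 could discard an informative interval.
- Take Week 12 benefit from the baseline-referenced BPI analyses already planned.

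Under this second route, for minimally important change, replace mean scores by the mean change in each scale over the same inter-visit interval that the rating covers. If the form is re-anchored, that interval runs from baseline. Either edit to the analysis text costs nothing in data collection.

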5.2 Clinical/Laboratory Criteria

- _____ a. Patients must be post-menopausal, as defined by at least one of the following:
 - 1. ≥ 12 months since the last menstrual period OR
 - 2. prior bilateral oophorectomy OR
 - 3. previous hysterectomy with one or both ovaries left in place (or previous hysterectomy in which documentation of bilateral oophorectomy is unavailable) AND (unless ≥ 60 years of age) FSH values consistent with the institutional normal values for the post menopausal state OR
 - 4. have been on LHRH agonist therapy for at least 3 months and estradiol levels drawn within 28 days prior to registration are consistent with the institutional normal values for post-menopausal state.
- _____ b. Patients must currently be taking one of the following aromatase inhibitor (AI) doses for at least 21 days prior to registration and plans to continue for at least an additional 180 days after registration. Patients may have received any number of prior AI therapies, but the first AI therapy must have started no more than 36 months prior to registration.
 - 1. anastrozole (Arimidex®) 1 mg daily
 - 2. letrozole (Femara®) 2.5 mg daily
 - 3. exemestane (Aromasin®) 25 mg daily

SWOG Patient No. _____

Patient's Initials (L, F, M) _____

- _____ c. Patients must have aromatase inhibitor (AI) associated musculoskeletal symptoms that began or increased after starting AI therapy. New musculoskeletal pain must not be due specifically to fracture or traumatic injury.
- _____ d. Patients must have completed the **S1202** Brief Pain Inventory-Short Form (BPI-SF) within 7 days prior to registration. Patients must have an "average pain" of at least 4 on the BPI-SF (item #4).
- _____ e. Patients must have Zubrod performance status of 0-2 (see [Section 10.3](#)).
- _____ f. Patients must have no known allergy or hypersensitivity to duloxetine or any of the inactive ingredients in the matching placebo.
- _____ g. Patients must not have any contraindicated concurrent illnesses listed on the duloxetine package insert including:
- Current primary psychiatric diagnosis (schizophrenia, psychosis) or suicidal ideation, history or bipolar disorder, or seizure disorder
 - History of alcohol or other substance abuse or dependence within 365 days prior to registration.
 - Chronic liver disease
 - End stage renal disease
 - Uncontrolled narrow-angle glaucoma
 - Clinically significant coagulation disorder

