Standard Deviation: Multiple studies of AI-induced joint pain have found the standard deviation for BPI “average pain” at follow-up on placebo to be about 2.0 to 2.5 points. [\(47,8\)](#) The design assumes a common standard deviation between arms; a similar standard deviation has been observed in a pilot study of duloxetine. [\(16\)](#) We assume a SD of 2.3 points at 12 weeks for this study (the estimated average SD found in Arnold, Clin J Pain, 2009). [\(8\)](#)

For a 1.0 point difference and a 2.3 point SD at 12 weeks, with other parameters as specified above, 270 eligible patients would be required for 80% power under a two-arm normal design. Power will be higher with lower observed standard deviation or a larger observed difference.

The following considerations clarify the impacts of loss, non-adherence, and contamination on the sample size calculations:

- A two-arm normal design with $\alpha=0.05$ two-sided test and a 2.3 point SD to detect a difference of 1.0 points requires approximately 166 patients (83 per arm) for 80% power.
- An estimated 5% non-adherence and 10% contamination both reduce the nominal effect size, from 1.0 points to 0.85 points. This increases the required sample size to 230 total patients (115 per arm).
- To account for an estimated 15% dropout rate, the total required sample size must be further increased by 15%, as in $230/0.85 = 270$ total patients.

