6. Reduces depression as measured by the Patient Health Questionnaire (PHQ-9). Differences between the two arms of at least five points on the PHQ-9 at 12 weeks will be of interest. (57) Clinically meaningful change in PHQ-9 scores will also be based on $\frac{1}{3}$ to $\frac{1}{2}$ of a standard deviation. (57)
 7. Decreases analgesic use.
 8. Increases adherence to, and reduces the discontinuation rate for, AI therapy.
 9. Affects measures of pain interference.
 10. Reasons for treatment discontinuation will also be described.
- c. Interaction tests between treatment and stratification variables will be conducted to explore whether these factors are predictive of average pain scores.
 - d. A logistic regression analysis of responders will be conducted, where a response to intervention is defined as a reduction of 2 or more points in average pain according to the BPI. (50)
 - e. In addition, we will explore the relationship between the severity of arthralgias and degree of benefit from therapy in each of the treatment groups and inherited variants in genes responsible for duloxetine metabolism and activity (COMT, HTR3A, SLC6A2, SLC6A4, CYP1A2, CYP2D6) and aromatase (CYP19A1). Finally, we will explore the relationship between baseline and change in serum inflammatory cytokine levels with 12 weeks of treatment and the degree of benefit from therapy in each of the treatment groups.

For linear scales, secondary endpoints will be analyzed using multiple linear regression analyses including the baseline score as a covariate and the pre-specified stratification factors. For binary outcomes, logistic regression will be used.

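### Section 11.3b.5 derives minimally important change from mean scores, although the rating that defines the groups asks about change since the previous questionnaire

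*Combined protocol and SAP*

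**What the plan says.** Section 11.3b.5 sorts patients by the Global Rating of Change (GRC) into worse (-1 to -3), same (0) and better (+1 to +3), judged "since the last time they completed the questionnaire". It then states: "Mean scores for the WOMAC Index, BPI, M-SACRAH, and FACT-ES TOI will be compared for groups based on those patients who select" the 'a little better' and 'a little worse' categories "on the GRC ratings to identify minimally important change".

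Section 15.2a confirms the reference period: the Global Ratings "are answered with respect to the last time the patient filled out the questionnaire". It also says that the scored questionnaires, including the four in this analysis, "should be rated with respect to the past 7 days".

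The last paragraph of 11.3 gives a general model for linear scales: "secondary endpoints will be analyzed using multiple linear regression analyses including the baseline score as a covariate and the pre-specified stratification factors". It does not say whether this covers the comparison of GRC groups.

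**The concern.** The grouping variable describes a change over an interval, while the quantity averaged within each group is a level at the end of it. Patients who have just improved may have started higher than those who have just worsened, so their current scores can lie closer together, or further apart, than their changes do. The result would be reported as minimally important change for four instruments without being a change.

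Two further details are left open. 'A little better' against 'a little worse' spans two steps of the rating with 'same' in between, and no rule says how the contrast becomes a minimally important change. The score interval is also not tied to the rating interval. The GRC is first given at Day 15 (Section 7.2b) and is not among the baseline forms (Section 7.2a), and Section 15.2 allows for missed forms. At stake is how the patient-reported scales are interpreted, not the test of efficacy.

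**Working it through.** The plan states no minimally important change, no between-visit correlation and no expected bias, so there is no figure to reproduce. The check asks how the planned contrast relates to the corresponding contrast in change.

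**Set-up.** Let X1 be the score at the previous form (SD s1), X2 the current score (SD s2), r their correlation and D = X2 - X1. If the rating depends on the scores only through D, and X2 is linear in D, then at a given visit

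ratio = (difference in mean score) / (difference in mean change) = Cov(X2, D) / Var(D) = (s2² - r·s1·s2) / (s1² + s2² - 2r·s1·s2).

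A ratio of 1 means that the score contrast equals the change contrast.

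**Equal SDs.** With s1 = s2 = s this is s²(1 - r) / [2s²(1 - r)] = 0.50 for any r.

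**Inputs.** The average-pain SDs come from Table 1 in Section 2.0 (open-label pilot, n = 29): 1.1 at baseline, 1.5 at week 2, 1.8 at week 6 and 1.6 at week 8. For the design SD, Section 11.1 says: "We assume a SD of 2.3 points at 12 weeks for this study". The range r = 0.3 to 0.7 is an assumption. The pilot ended at week 8, so weeks 6 to 8 stand in for weeks 6 to 12.

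**Worked at r = 0.5.**
- 1.1 to 1.5: (2.25 - 0.825) / (1.21 + 2.25 - 1.65) = 1.425 / 1.81 = 0.79
- 1.5 to 1.8: (3.24 - 1.35) / (2.25 + 3.24 - 2.70) = 1.89 / 2.79 = 0.68
- 1.8 to 1.6: (2.56 - 1.44) / (3.24 + 2.56 - 2.88) = 1.12 / 2.92 = 0.38
- 1.1 to 2.3: (5.29 - 1.265) / (1.21 + 5.29 - 2.53) = 4.025 / 3.97 = 1.01

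| Interval (average pain) | s1, s2 | r = 0.3 | r = 0.5 | r = 0.7 |
|---|---|---|---|---|
| Equal SDs | 2.3, 2.3 | 0.50 | 0.50 | 0.50 |
| Baseline to week 2 | 1.1, 1.5 | 0.71 | 0.79 | 0.95 |
| Week 2 to 6 | 1.5, 1.8 | 0.63 | 0.68 | 0.79 |
| Week 6 to 8 | 1.8, 1.6 | 0.42 | 0.38 | 0.31 |
| Pilot baseline to design SD | 1.1, 2.3 | 0.91 | 1.01 | 1.19 |

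**Against a one-step target.** A simulation (1,000,000 patients, seven-level rating with noise, r = 0.5, rating driven by change alone) compared the score contrast with the mean change from 'same' to the adjacent category.

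| s1, s2 | Score contrast | Two-step change | One-step change | Score / one-step |
|---|---|---|---|---|
| 2.3, 2.3 | 1.23 | 2.46 | 1.23 | 1.00 |
| 1.1, 1.5 | 0.99 | 1.25 | 0.63 | 1.57 |
| 1.5, 1.8 | 1.13 | 1.67 | 0.83 | 1.35 |
| 1.8, 1.6 | 0.66 | 1.72 | 0.86 | 0.77 |
| 1.1, 2.3 | 2.09 | 2.07 | 1.03 | 2.03 |

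**If the rating also reflects the current state.** With an assumed weight of 0.3 to 0.5 on the current score, the simulated ratio to the two-step change contrast was 0.65 to 1.44.

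**The case against.** **The plan may already mean change.** The sentence aims at minimally important change, groups patients by a change rating and cites sources for the method, so 'scores' may be shorthand for change scores. That is possible, but the text does not say so, and an analyst following it literally would compare levels.

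**The general model adjusts for baseline.** In the simulations, adjusting for the score at the previous visit brought the ratio to 0.87 to 1.00 when the rating reflected change alone (0.86 to 1.20 over all cases). This helps only in part. The paragraph is not stated to cover the GRC comparison, and baseline is the previous assessment only for the Day 15 rating. With no missed form, the Day 43 and Day 85 ratings look back to Days 15 and 43.

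**The result may carry little weight.** Section 11.3b already names two points for the WOMAC and M-SACRAH, and one third to one half of an SD for those scales and the FACT-ES TOI. Section 11.1 cites two points as meaningful individual change on the BPI, and 11.3d uses two points to define response. Nothing says that the anchor estimate replaces these. The GRC sits among the exploratory objectives (Section 1.3g). This stands and limits the severity.

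**A stronger reading that the documents do not support.** A reader might infer that the plan understates minimally important change by about half, so that trivial differences would later be called meaningful. That needs equal SDs at both visits, a rating driven only by change, no adjustment for the earlier score, and the two-step contrast as target. The entry floor of 4 on average pain (Section 5.2d) and the pilot SDs argue against equal SDs over the first interval. Even with equal SDs, the score contrast (1.23) equals the one-step change from 'same' (1.23), so against that target there is no understatement.

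**Conclusion.** The mismatch is real as the text is written: a rating of change is paired with mean levels, and no other section clearly repairs it. What the contrast estimates depends on the SDs at both visits, their correlation and how patients use the rating. For average pain, with the pilot and design SDs and r assumed at 0.3 to 0.7, it is about 0.3 to 1.2 times the matching change contrast. The result also rests on approximate linearity and on SDs from a small single-arm pilot. Neither size nor direction can be asserted in advance. Severity is minor: the analysis is secondary and interpretive, and the primary test, the main secondary outcome and the sample size do not depend on it.

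**What to change.** In Section 11.3b.5, replace 'Mean scores' with 'Mean change since the previous completed questionnaire', summarised by GRC category. Compare 'a little better' with 'same' (score 0) for improvement, and 'a little worse' with 'same' for worsening. Add that the Day 15 rating is matched to change from the pre-treatment forms, since no earlier Global Rating exists, and that after a missed form the change runs from the last one completed.

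The cost is a sentence or two. All the scores and ratings are already collected. If change scores were intended all along, the edit only makes that explicit.
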